# 7.5 Blinding

This is an open-label study. Neither the patient, the Investigator/site staff, nor the Sponsor will be blinded to the treatment administered.

## 7.6 **Prior treatment**

Reasonable efforts will be made to determine all relevant prior treatments received by the patient within 30 days prior to the first derazantinib dose, including accurate start and stop dates of the regimens. All relevant information must be recorded in the appropriate patient's eCRF. All surgical procedure history, prior chemotherapy, and radiation therapy must be recorded on the appropriate eCRF.

## 7.7 Concomitant treatments

All information regarding concomitant treatments (medications or procedures) must be recorded on the patient's eCRF (including the name of the medication or procedure and duration of treatment). Complete information of analgesics and acid-reducing agents' consumption should be obtained and recorded.

#### 7.7.1 **Permitted treatment**

Palliative and supportive care for disease-related symptoms will be offered to all patients. In addition, the following treatments are allowed:

- Standard therapies for concurrent medical conditions
- Erythropoietin Stimulating Agents (ESA): Please follow the American Society of Clinical Oncology (ASCO), the American Society of Hematology, MEDICARE guidelines for the use of epoetin in patients with cancer and Food and Drug Administration (FDA) alerts dated 09 March 2007, 08 November 2007, 12 March 2008, 31 July 2008, and 02 December 2008.
- Hematopoietic growth factors, including filgrastim (Neupogen®), or other granulocyte colony stimulating factors (G-CSF). Please follow ASCO guidelines for the use of white blood cell growth factors (http://jco.ascopubs.org/content/24/19/3187.full).
- Prophylactic antiemetics may be administered according to standard practice
- Megestrol acetate (Megace®)
- Use of topical corticosteroids, topical and systemic antibiotics according to standard of care (SOC) or institutional guidelines
- Treatment with non-conventional therapies (i.e., herbs or acupuncture) and vitamin/mineral supplements are acceptable, provided that they do not interfere with the study endpoints, in the opinion of the Investigator
- Bisphosphonates and denosumab for bone metastases or hypercalcemia of malignancy
- Palliative radiotherapy for non-hepatic local pain control provided that, in the opinion of the Investigator, the patient does not meet the criteria for treatment discontinuation (i.e., clear progression of disease)

#### 7.7.2 Prohibited treatment / treatment to be avoided or used with caution

The following treatments are not allowed during the study:

- Any concurrent anti-cancer therapy including chemotherapy, radiotherapy, hormonal, targeted therapy, or immunotherapy
  - Palliative radiotherapy for non-hepatic local pain-control may be allowed, provided the patient does not meet criteria of progressive disease and treated lesions will not be included in the target/non-target lesion assessment
- Other investigational agents
- Immunosuppressive therapies, including systemic corticosteroids (except up to a 25 mg/day prednisone-equivalent dose or when used intermittently in an antiemetic regimen, for CNS metastases management or as premedication for imaging studies)

The following treatments should be avoided, if possible, or used with caution during the study:

- Derazantinib may inhibit CYP2C8, CYP1A2, or CYP2D6 metabolism, hence coadministration of derazantinib with drugs known to be substrates of CYP2C8, CYP1A2, or CYP2D6 should be avoided or used with caution (see Appendix 4)
- Derazantinib may be a substrate and inhibitor of human P-glycoprotein (P-gp), therefore co-administration of derazantinib with drugs known to be P-gp substrates with narrow therapeutic index should be avoided or used with caution (see Appendix 5)
- Drugs with known liver toxicity, e.g., clotrimazole, should be avoided or used with caution; if such drugs need to be administered, LFT should be done every 4–5 days during the drugs' co-administration
- Drugs with the potential to prolong QT interval (see Appendix 9)

#### 7.8 Potential risks and benefits for study participants

Derazantinib, a multi-kinase inhibitor with activity against FGFR1, FGFR2, mutant FGFR2, FGFR3, and mutant FGFR3 kinases, has demonstrated efficacy and an acceptable safety profile in nonclinical studies. In clinical trials in iCCA (Mazzaferro 2018, Papadopoulos 2017, Droz dit Busset 2020), derazantinib has been shown to be active with a manageable safety profile. It is therefore expected that patients may derive a benefit from derazantinib monotherapy in the current study.

Hyperphosphatemia, fatigue, ocular disorders, gastrointestinal disorders (constipation, diarrhea, nausea, vomiting, stomatitis, and dry mouth), transaminase elevation, hypertension, creatinine increased / renal disorders, hyponatremia, nail toxicities and alopecia are the most frequently reported adverse drug reactions (ADRs) with FGFR inhibitor treatments (Chae 2017, Katoh 2019, Balversa® USPI, Pemazyre® USPI), and are considered to be FGFR inhibitor class effects. Of these, hyperphosphatemia, fatigue, ocular disorders, blood creatinine increased/renal disorders, hyponatremia, and nail toxicities are assessed as important potential risks for derazantinib, and increased transaminases is assessed as an important identified risk for derazantinib. The following events are assessed as potential risks for derazantinib: QT prolongation, gastrointestinal disorders, hypertension, and alopecia. Gastrointestinal disorders, and hypertension can be monitored

and are mostly manageable, and the event alopecia has no significant impact on the condition of the patients. Non-clinical and clinical data on QT prolongation rule out a large (i.e., mean effect > 20 ms) effect of derazantinib on QTcF. There have been no serious events / arrhythmias reported as being consequent to QT prolongation, and the risk is mostly preventable with the implemented routine risk minimization measures. As the safety data are accumulating and remain subject to final evaluation for ongoing studies with derazantinib, the Sponsor will continue to evaluate safety data to characterize further potential risks and assess identified risks.

## 8 SAFETY ASSESSMENTS

#### 8.1 **Definitions**

#### 8.1.1 Adverse events

An AE is defined as any untoward medical occurrence in a patient or clinical investigational subject administered a pharmaceutical product, and that does not necessarily have a causal relationship with study-drug treatment. An AE can therefore be any unfavorable and unintended sign (including an abnormal laboratory finding, for example), symptom, or disease temporally associated with the use of a medicinal product, whether or not considered related to the medicinal product.

#### 8.1.2 Serious adverse events

An SAE is any adverse experience occurring at any dose that results in any of the following outcomes:

- Death
- Life-threatening
- Requires new inpatient hospitalization defined as a hospital admission lasting > 24 hours (not including emergency room visit without hospital admission), or prolongation of existing hospitalization
- Persistent or significant disability/incapacity
- Congenital anomaly/birth defect
- Other important medical event that may not be immediately life-threatening or result in death or hospitalization but may jeopardize the patient or may require intervention to prevent one of the other outcomes listed above. An important medical event may be considered an SAE based upon appropriate medical judgment.

#### 8.1.3 Unexpected adverse event or serious adverse event

An unexpected AE or SAE is one for which the nature or severity of the event is not consistent with the applicable product information, as summarized in the Investigator's Brochure.

#### 8.1.4 Suspected unexpected serious adverse reactions

All AEs that are determined by the Investigator or by the Sponsor as having a reasonable suspected causal relationship to a study drug and that are both unexpected and serious are considered to be suspected unexpected serious adverse reactions (SUSARs), and are subject to expedited regulatory reporting.

#### 8.1.5 Inpatient hospitalization

An inpatient hospitalization is a hospital admission that lasts more than 24 hours.

#### 8.1.6 Study drug-related adverse event or serious adverse event

A study drug-related AE or SAE is defined as an AE or SAE that is definitely, probably, or possibly related to the treatment with derazantinib, or when the relationship is unknown.

#### 8.1.7 Further adverse event and serious adverse event definitions

Wherever possible, a specific disease or syndrome rather than individual associated signs and symptoms should be identified. However, if an observed or reported sign or symptom is not considered a component of a specific disease or syndrome by the Investigator, it should be recorded as a separate AE.

Laboratory data are to be collected as stipulated in Section 6.5. Clinical syndromes associated with laboratory abnormalities are to be recorded as appropriate (e.g., diabetes mellitus instead of hyperglycemia).

Scheduled hospitalizations or elective surgical for a pre-existing condition that is unrelated to the disease under study and has not worsened are not considered SAEs.

Prolongation of a scheduled hospitalization is considered an SAE.

Complications associated with scheduled procedures are considered AEs or SAEs.

Progression of disease is considered an efficacy outcome parameter and should not be captured as an AE or SAE unless its outcome is death.

Adverse events, that occur following the execution of the ICF but prior to dosing must be recorded in the medical history page of the eCRF; if serious, these must be reported as SAEs as described in Section 8.4. Adverse events, including SAEs, that occur after patients receive any anti-cancer therapy in the follow-up period, other than the study-defined treatments, will not be recorded as AEs or SAEs.

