#### 5.5 **30-day Safety Follow-up visit**

All patients will be followed for a minimum of 30 days after the last dose of derazantinib. During the 30-day safety follow-up period, AEs and changes in concomitant medication should be reported.

Patients with unresolved study drug-related AEs (occurred during the study treatment period or the 30-day safety follow-up period) will be followed until, in the opinion of the Investigator, study drug related toxicities have resolved to baseline, CTCAE Grade 1, stabilized, or are deemed to be irreversible. A study drug-related AE is defined as an AE that is definitely, probably, or possibly related to the treatment with derazantinib, or when the relationship is unknown. If a patient receives other anti-cancer therapy within the 30-day safety follow-up period, the follow-up for AEs will cease, beginning the first day of the new therapy.

\* Patients who develop ocular symptoms or changes in visual acuity while on the study should be referred to an ophthalmologist for a complete eye examination.

In addition, at the 30-day Safety Follow-up visit, the following assessments will be made:

- EORTC QLQ-C30 and QLQ-BIL21, and EQ-5D, questionnaires (should be completed by the patient prior to being evaluated by the physician) (see Section 6.10 and Appendix 7)
- Physical examination (see Section 6.2)
- Complete opthalmological examination (see Section 6.3)
- Vital signs (weight, temperature, blood pressure, respiration rate, and pulse)
- ECOG performance status (see Appendix 2)
- Clinical blood tests (see Section 6.5)
- Serum- or urine pregnancy testing (to be performed monthly until 120 days after the last administration of study drug) (see Section 8.8.2)

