#### 8.2 **Responsibilities and procedures**

The responsibility for the safety of an individual patient lies in all cases with the Investigator. This includes the timely review of all safety data obtained during the course of the study.

An Investigator must instruct his/her patients to report any AE and SAE they experience.

Investigators capture, evaluate, and document all AEs and SAEs occurring during a patient's enrollment in the study, commencing with the first day of treatment and including the protocol-defined 30-day post-treatment follow-up period, as source documents and on designated eCRF pages. SAEs related to study-specific procedures (e.g., tissue biopsy) will be reported from the date of signing the informed consent.

Investigators should assess AEs at each scheduled and non-scheduled visit, by the use of open-ended questioning, physical examination, and review of laboratory results.

Note: It is important to record all AEs and SAEs that result in temporary and permanent discontinuation of study drug, regardless of severity.

Investigators must report all SAEs, whether or not they are considered study-drug related, to the Sponsor or designee within 24 hours from knowledge of the event (see Section 8.4).

[figure not shown]
In cases of SUSARs, Investigators are responsible for reporting to their local IRB/IEC; the Sponsor or designee(s) is responsible for notifying regulatory authorities and all relevant Investigators.

[figure not shown]

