# 8.5 **Post-treatment safety follow-up**

In this study, the post-treatment safety follow-up period is defined as at least 30 days after the last dose of assigned treatment.

All patients will be followed for a minimum of 30 days after discontinuation of the study drug. However, if a patient receives other anticancer therapy within the 30-day follow-up period, the follow-up for AEs will cease, beginning on the first day of the new therapy. Note: Survival follow-up will continue.

Unresolved study-drug-related AEs and SAEs at the end of the 30-day safety follow-up period will be followed until they have, in the opinion of the Investigator, resolved to baseline or CTCAE Grade 1, stabilized, or are deemed to be irreversible.

After the follow-up period, only study-drug-related SAEs must be collected and reported; these must also be followed until they have, in the opinion of the Investigator, resolved to baseline or CTCAE Grade 1, stabilized, or are deemed to be irreversible.

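### Protocol 8.1.7 and 8.5 give opposite instructions for a drug-related SAE arising after the follow-up period in a patient who began new anti-cancer therapy during it

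*Protocol*

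**What the plan says.** **End of the window.** Protocol 8.1.7 states that adverse events, serious ones included, arising "after patients receive any anti-cancer therapy in the follow-up period, other than the study-defined treatments, will not be recorded as AEs or SAEs". It makes no exception by causality. Protocol 8.5 sets the period: "the post-treatment safety follow-up period is defined as at least 30 days after the last dose of assigned treatment". Thirty days is therefore a minimum. If another anticancer therapy is given within those 30 days, "the follow-up for AEs will cease, beginning on the first day of the new therapy"; Protocol 5.5 says the same ("If a patient receives other anti-cancer therapy within the 30-day safety follow-up period, the follow-up for AEs will cease"). For the time beyond, 8.5 says: "After the follow-up period, only study-drug-related SAEs must be collected and reported". It gives no end date and no exception for new therapy. Under 8.1.6, an event whose relationship is unknown counts as drug-related.

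Both 5.5 and 8.5 also ask that unresolved drug-related events be followed until they settle, stabilise or are judged permanent.

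**Start of the window.** For events between consent and first dose, 8.1.7 says "if serious, these must be reported as SAEs as described in Section 8.4", whatever the cause. Protocol 8.2 starts AE and SAE capture on the first day of treatment and adds: "SAEs related to study-specific procedures (e.g., tissue biopsy) will be reported from the date of signing the informed consent". Elsewhere 8.2 asks investigators to report all SAEs, and 8.4 asks for each SAE during the investigation within 24 hours, related or not.

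No section says which rule prevails.

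**The concern.** Patients who stop derazantinib on progression are natural candidates for a further line of therapy soon afterwards. If such a patient later has a serious event attributed to derazantinib, or one whose cause cannot be settled, 8.5 tells the site to report it and 8.1.7 tells the site not to record it. Different sites can comply with the protocol and do opposite things.

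What is at stake is safety reporting. The sponsor can identify a suspected unexpected serious reaction (8.1.4, 8.4) only if the site sends the event. The SAP's by-patient SAE listing (3.2.8.1) can show only what was collected. Protocol 7.8 names increased transaminases as an important identified risk and ocular disorders as an important potential risk, so late related events are worth capturing under one rule.

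Before dosing, a serious event that is not procedure-related is plainly reportable under 8.1.7 but falls outside the capture window described in 8.2.

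**Working it through.** There is no plan figure to reproduce. The check sets the rules side by side for each timing of a serious event.

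| Case | 8.1.7 | 8.5 and 5.5 | 8.2 and 8.4 | Result |
|---|---|---|---|---|
| 1. After consent, before dose, not procedure-related | Report | Silent | Outside 8.2's capture window; within the general wording of 8.2 and 8.4 | Inconsistent |
| 2. After consent, before dose, procedure-related | Report | Silent | Report | Consistent |
| 3. Within 30 days of last dose, no new therapy | No bar | Within safety follow-up | Report | Consistent |
| 4. Within 30 days, new event after new therapy has started | Do not record | AE follow-up stops | General wording still asks for all SAEs | 5.5, 8.5 and 8.1.7 agree |
| 5. Drug-related, after the follow-up period, new therapy begun during it | Do not record | 8.5: collect and report | 8.4: report | **Direct conflict** |
| 6. Drug-related, after the follow-up period, new therapy begun after day 30 | Depends on what the follow-up period means in 8.1.7 | 8.5: collect and report | 8.4: report | Conflict only if the term reaches into survival follow-up |

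**Case 5 by example.** Last dose on day 0, next line begun on day 8, drug-related SAE on day 40. The therapy began in the follow-up period and the event came after it, so 8.1.7 says not recorded. Day 40 is beyond the 30-day period and the event is drug-related, so 8.5 says collect and report.

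**Case 4.** The agreement holds if the follow-up period runs its full 30 days. If it were read as ending on the day new therapy starts, the 8.5 duty would begin at once and the conflict would move into the 30 days. The text does not clearly support that reading.

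**Effect on planned tables.** Protocol 10.3 and SAP 3.2.8.1 both end the TEAE window for new events at 30 days or at new anticancer therapy, whichever is earlier. Case 5 events are outside that window under either rule, so the TEAE tables do not change.

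**Rough size.** Protocol 1.5.3 reports drug-related SAEs in 4 of 119 patients in the earlier Phase 1/2 study: 4 / 119 = 3.4%. Planned enrolment here is about 100 + 43 = 143. If the same rate applied (an assumption), 143 × 4 / 119 = 4.8, or about 5 patients with any drug-related SAE. Case 5 would be a subset of patients like these. This is a guide and not a bound: the earlier study's collection window is not given here, so late events may have been missed there too. The documents do not say what share of patients start another therapy within 30 days.

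**The case against.** The strongest reply is that the plan is mostly coherent. Inside the 30 days, 5.5, 8.5, 8.1.7, 10.3 and the SAP all stop new-event collection at new therapy. That stands, and it limits the point to case 5 and possibly case 6. A reader might infer that every drug-related SAE after the next therapy is caught between two rules; the text does not support that.

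A reader might also infer that unresolved drug-related AEs are both owed follow-up and dropped. This is not a clear contradiction. In 5.5 the stop directly follows the duty and can be read as its exception. In 8.5 the duty applies to events unresolved at the end of the 30 days. Also, 8.1.7 bars only events that occur after the new therapy. What remains is that neither 5.5 nor 8.5 says whether the stop covers events already open.

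A third inference is that 10.3 cannot be met, because it counts events later judged drug-related through the end of the study. That clause can be read as covering only events present at baseline, so it does not show a need for new late events.

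At the start of the window, 8.2 never limits pre-dose reporting to procedure-related SAEs in so many words, and the general wording of 8.2 and 8.4 asks for all SAEs. So 8.1.7 can be read as the specific pre-dose rule. The inconsistency is real but softer than at the end of the window.

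Finally, it is tempting to size the problem by everyone who starts another therapy, or everyone tested for *FGFR2* status. Neither count measures it: the rules differ only for a person who has a relevant SAE.

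**Conclusion.** The conflict in case 5 is certain on the current text and needs no special reading of any term. Case 6 is conditional on the undefined follow-up period in 8.1.7. The pre-dose inconsistency in case 1 is present but softer, and the treatment of already unresolved drug-related AEs is unclear rather than contradictory.

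Few events are likely to be involved, and their number cannot be derived from the documents. There is no effect on alpha, power, endpoints or the planned TEAE tables. The effect is on SAE collection, expedited reporting and SAE listings. The point should be corrected because the events concerned are serious and attributed to the drug or of unknown cause, and because the correction is cheap.

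**What to change.** 1. In 8.1.7, add an exception for study-drug-related SAEs, so that the duty in 8.5 holds whether or not new therapy has started, and have the start date of the new therapy recorded with the event. The wording should also say whether the exception covers the days between new therapy and day 30, where 5.5 and 8.5 now stop.
2. In 5.5 and 8.5, state whether the stop at new therapy applies to drug-related AEs already unresolved on that date.
3. Separately, reconcile 8.1.7, 8.2 and 8.4 into one pre-dose rule. The documents do not show which scope was intended. Narrowing to procedure-related SAEs would remove reports that 8.1.7 now requires and would clash with 8.4, so the narrower rule should not be adopted by default.

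The cost is a few sentences of protocol text and matching eCRF completion guidance. The downside is a few late reports whose causality is confounded by the new therapy; the recorded start date helps in judging them.

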#### 8.2 **Responsibilities and procedures**

The responsibility for the safety of an individual patient lies in all cases with the Investigator. This includes the timely review of all safety data obtained during the course of the study.

An Investigator must instruct his/her patients to report any AE and SAE they experience.

Investigators capture, evaluate, and document all AEs and SAEs occurring during a patient's enrollment in the study, commencing with the first day of treatment and including the protocol-defined 30-day post-treatment follow-up period, as source documents and on designated eCRF pages. SAEs related to study-specific procedures (e.g., tissue biopsy) will be reported from the date of signing the informed consent.

Investigators should assess AEs at each scheduled and non-scheduled visit, by the use of open-ended questioning, physical examination, and review of laboratory results.

Note: It is important to record all AEs and SAEs that result in temporary and permanent discontinuation of study drug, regardless of severity.

Investigators must report all SAEs, whether or not they are considered study-drug related, to the Sponsor or designee within 24 hours from knowledge of the event (see Section 8.4).

[figure not shown]
In cases of SUSARs, Investigators are responsible for reporting to their local IRB/IEC; the Sponsor or designee(s) is responsible for notifying regulatory authorities and all relevant Investigators.

[figure not shown]
